# 1.3.1. Schedule of Activities – Screening Phase and Induction Phase

Study Phase	Screening	Study Intervention						Open-label Induction Phase a						
Visit Day (D)/Week (W) b	W 4 to 0°	D1 d	W2	W4	W6	W8	W12	W16	W20	W24	W28	W32	End of induction phase (≥W36) b /C D1 e /WD f	
Study Day (Window)	28 to 0	1	15 +/ 2d	29 +/ 2d	43 +/ 2d	57 +/ 2d	85 +/ 2d	113 +/ 3d	141 +/ 3d	169 +/ 3d	197 +/ 3d	225 +/ 3d	253 +/ 3d	
Screening/Administrative														
ICFg	X													
ICF for optional pharmacogenomic samples	X													
Inclusion/exclusion criteria	$X^h$												X nn	
Prestudy therapy (including prior anti HBV therapy)	X													
Medical/surgical history and demographics i	X													
Preplanned surgery/procedure(s)	X													
Fibroscan or liver biopsy j	X													
Ultrasound k	X													
Serum IgM anti HBc antibody test	X													
HBV genotype 		X												
Study Intervention														
Enrollment without randomization pp		X												
Administer JNJ 3989		X		X		X	X	X	X	X	X	X	X e,m	
Intake of NA n		X	X	X	X	X	X	X	X	X	X	X	Xe,m	
Intake of JNJ 6379 (stopped per Amendment 6) rr		X	X	X	X	X	X	X	X	X	X	X	X	
Dispense NA		X		X		X	X	X	X	X	X	X	X m	
Dispense JNJ 6379 (stopped per Amendment 6) rr		X		X		X	X	X	X	X	X	X	X	
Administer/dispense PegIFN α2a n													X b,e,m	
Study intervention accountability				X		X	X	X	X	X	X	X	X	
Safety Assessments														
Complete physical examination o	X									X			X	
Body weight and Symptom directed physical examination		X	X	X	X	X	X	X	X		X	X		
Ophthalmic examination p	X											(X)p	(X) p	

Study Phase	Screening				Study	Interv	ention	Open	-label I	nducti			
Visit Day (D)/Week (W) b	W 4 to 0°	D1 d	W2	W4	W6	W8	W12	W16	W20	W24	W28	W32	End of induction phase (≥W36) b /C D1 e /WD f
Study Day (Window)	28 to 0	1	15 +/ 2d	29 +/ 2d	43 +/ 2d	57 +/ 2d	85 +/ 2d	113 +/ 3d	141 +/ 3d	169 +/ 3d	197 +/ 3d	225 +/ 3d	253 +/ 3d
Vital signs q	X	X	X	X	X	X	X	X	X	X	X	X	X
Triplicate 12 lead ECG r	X	X		X			X			X			X
Injection site reactions			X	X	X	X	X	X	X	X	X	X	X
Liver ultrasound		(X)°°								X s			X s
Clinical Laboratory Tests													
Hematology u	X	X	X	X	X	X	X	X	X	X	X	X	X
Blood chemistry (including liver function tests) t,v,w	X	X	X	X	X	X	X	X	X	X	X	X	X
Blood coagulation	X	X		X		X	X	X	X	X	X	X	X
Urinalysis x	X	X		X		X	X	X	X	X	X	X	X
Urine chemistry y	X	X		X		X	X	X	X	X	X	X	X
Renal biomarkers 		X					X			X			X
Testing for hepatitis A, B, C, D, and E virus, HIV 1 and 2 w	X												
FSH test (postmenopausal women only)bb	X												
AFP test w,aa	X									X			X
Hemoglobin A1c test	X												
Serum pregnancy test (women of childbearing potential only)	X												
Urine pregnancy test (women of childbearing potential)		X		X		X	X	X	X	X	X	X	X
TSH and T4	X											X	
Efficacy Evaluations													
Fibroscance		(X)											(X)
HBV Virology													
Blood sampling for HBV DNA	X	X	X	X	X	X	X	X	X	X	X	X	X
Blood sampling for HBV RNA dd	X	X	X	X	X	X	X	X	X	X		X	X
Sampling for viral genome sequencingee	X	X		X			X		X			X	X
HBV Serology													
Blood sampling for:													
Anti HBs and anti HBe	X	X								X			X
HBsAg and HBeAg (qualitative)	X	X								X			X
HBsAg and HBeAg (quantitative)	X	X	X	X	X	X	X	X	X	X	X	X	X
HBcrAg dd	X	X	X	X	X	X	X		X	X		X	X
Exploratory serologyff	X	X	X	X	X	X	X	X	X	X		X	X

CONFIDENTIAL – FOIA Exemptions Apply in U.S. Status: Approved, Date: 25 November 2021

Study Phase	Screening				Study	Interv	ention	Open	-label I	nductio	on Phas	e a	
Visit Day (D)/Week (W) b	W 4 to 0°	D1 d	W2	W4	W6	W8	W12	W16	W20	W24	W28	W32	End of induction phase (≥W36) b /C D1 e /WD f
Study Day (Window)	28 to 0	1	15 +/ 2d	29 +/ 2d	43 +/ 2d	57 +/ 2d	85 +/ 2d	113 +/ 3d	141 +/ 3d	169 +/ 3d	197 +/ 3d	225 +/ 3d	253 +/ 3d
Clinical Pharmacology Assessments													
Blood sampling for sparse PK of JNJ 3989, NA and PegIFN α2agg		Xhh		Xhh			Xhh			X hh,jj			X hh
Blood sampling for intensive PK of JNJ 3989, NA and PegIFN α2a (PK substudy) ii										X			
Exploratory Host Biomarkers													
Whole blood RNA gene expression		X					X			X			X
Whole blood single cell profiling		X				X				X			X
Host serum proteins (eg, cytokines)		X	X	X	X	X	X			X		X	X
Antidrug antibodies (to JNJ 3989)		X				X		X		X		X	X
Immune Monitoring													
Immune cells (PBMCs) (selected sites only)kk		X								X			X
Pharmacogenomics (DNA)													
HLA typing		X											
Exploratory host genotyping (optional) II		X											
Epigenetic research (optional) 										X			X
PRO Evaluations													
SF 36v2		X								X			X
HBQOL		X								X			X
EQ 5D 5L		X								X			X
PGIC										X			X
Ongoing Participant Review													
Concomitant therapy mm	X	X	X	X	X	X	X	X	X	X	X	X	X
Adverse events mm,qq	X	X	X	X	X	X	X	X	X	X	X	X	X

General Note: The PRO assessments and ECGs should be completed before any tests, procedures or other consultations for that visit.

AFP: Alpha fetoprotein; ALP: alkaline phosphatase; ALT: alanine aminotransferase; AST: aspartate aminotransferase; C: consolidation; CKD EPI: Chronic Kidney Disease Epidemiology Collaboration; CRF: case report form; CT: computed tomography; D: days; DAIDS: Division of Acquired Immunodeficiency Syndrome; DBP: diastolic blood pressure; DNA: deoxyribonucleic acid; ECG: electrocardiogram; eGFR: estimated glomerular filtration rate; EQ 5D 5L: 5 Level EuroQol 5 Dimension; FSH: follicle stimulating hormone; GI giga; HBc: hepatitis B core protein; HBe(Ag): hepatitis B e (antigen); HBcrAg: hepatitis B core related antigen; HLA: human leukocyte antigen; HBQOL: Hepatitis B Quality of Life; HBs(Ag): hepatitis B surface (antigen); HBV: hepatitis B virus; HCC hepatocellular carcinoma; HIV 1 (2): human immunodeficiency virus type 1 (type 2); ICF: informed consent form; IgM: immunoglobulin M; ISA: intervention specific appendix; MRI: magnetic resonance imaging; NA: nucleos(t)ide analog; PBMC: peripheral blood mononuclear cells; PegIFN a2a: pegylated interferon alpha 2a; PGIC: Patient Global Impression of Change; PK: pharmacokinetic; PRO: patient reported outcome; RBC: red blood cell; RNA: ribonucleic acid; SBP: systolic blood pressure; SF 36v2: Short Form 36 version 2; T4: thyroxine; TSH: thyroid stimulating hormone; ULN: upper limit of normal; W: Week; WD: withdrawal.

a. All study visits are to be scheduled relative to the baseline (Day 1) visit date.

- b. All participants will have an end of induction phase visit at Week 36 (or later if they already passed the Week 36 visit at the time of Protocol Amendment 5) and enter the consolidation phase. Participants enrolled before Protocol Amendment 5 is in effect will switch to the new study design as soon as Protocol Amendment 5 is in effect. Participants who did not yet reach the Week 36 visit at that time will have PegIFN α2a added to their treatment regimen at Week 36 for 12 weeks. Participants who already passed the Week 36 visit and/or were randomized to the group without PegIFN α2a, will have PegIFN α2a added to their treatment regimen at the next scheduled visit.
- c. If necessary (eg, for operational reasons), the screening phase may be extended up to a maximum of 6 weeks in agreement with the sponsor.
- d. Day 1 samples are to be collected before the first dose of study intervention.
- e. The end of induction phase visit is equivalent to Day 1 of the consolidation phase (C D1). All assessments (with the exception of the sparse PK sample, which should be taken 2 8 hours after JNJ 3989 dosing) should be performed before administration/intake of JNJ 3989, PegIFN α2a, and NA. PegIFN α2a should be administered weekly, preferably in the evening by self injection. If desired, participants can also choose to have the administration of PegIFN α2a performed on site irrespective of the time of day.
- f. Participants who discontinue study intervention early will have an early WD visit and will enter follow up (see the Schedule of Activities Follow up Phase) unless they withdraw consent. Participants who withdraw consent will be offered an optional safety follow up visit to occur on the day of consent withdrawal. For the optional safety follow up visit, assessments are at the investigator's discretion and could be similar to the early WD visit.
- Both the Platform Master ICF and the ISA ICF must be signed before the first study related activity.
- h. Minimum criteria for the availability of documentation supporting the eligibility criteria are described in the source documents section in Attachment 3 of the Master Protocol PLATFORMPAHPB2001. Clinical status will be checked at screening and again before first dose of study intervention. If a participant's clinical status changes (including any available laboratory results or receipt of additional medical records) after screening but before the first dose of study intervention is given such that he or she no longer meets all eligibility criteria, then the participant should be excluded from participation in the study.
- i. Medical history also includes mode of HBV transmission, stage of liver fibrosis, and alcohol consumption. Historical HBV DNA, ALT, HBsAg, and HBeAg data if available, will be recorded in the CRF and/or source documents. Available historical data on previous HBV genotype assessments will also be collected in the CRF.
- j. Liver disease staging assessments will be performed based on Fibroscan or liver biopsy results, obtained within 6 months (in case of Fibroscan) or within 1 year (in case of liver biopsy) prior to screening or at the time of screening.
- k. Participants must have absence of signs of cirrhosis or portal hypertension (absence of nodules, smooth liver contour, normal portal vein, spleen size <12 cm) and absence of signs of HCC or clinically relevant renal abnormalities on an abdominal ultrasound performed within 6 months prior to screening or at the time of screening. In case of suspicious findings on conventional ultrasound the participant may still be eligible if HCC or clinically relevant renal abnormalities have been ruled out by a more specific imaging procedure (contrast enhanced ultrasound, CT or MRI).
- HBV genotype will be determined at baseline using a standard genotyping assay if HBV DNA levels are sufficiently high. In virologically suppressed participants, available historical data on a previous HBV genotype assessment will also be collected in the CRF. Exploratory genotyping may be performed.
- m. Not applicable for the WD visit.

- n. In between study visits, participants will take NA orally at home and will bring their NA with them to each study visit. At study visits, NA should be taken on site. PegIFN α2a should be administered weekly, preferably in the evening by self injection. If desired, participants can also choose to have the weekly administration of PegIFN α2a performed on site irrespective of the time of day.
- o. Complete physical examination, including height (only at screening), body weight, skin examination, and other body systems.
- p. For participants with a risk factor (eg, diabetes or hypertension), an ophthalmic examination at Week 32 of the induction phase should be considered. Any participant experiencing a decrease or loss of vision at any time point during study participation, must have a prompt ophthalmic examination.
- q. Vital signs include supine SBP, DBP, pulse rate, and body temperature.
- r. All ECGs will be read centrally. In addition, on Day 1, the ECG will be collected and assessed locally prior to dosing. ECGs should be completed before any tests, procedures or other consultations for that visit.
- s. A liver ultrasound is recommended every 6 months for HCC screening in high risk populations (ie, participants with a family history of HCC, Asian males >40 years, Asian females >50 years; or African/African American males >40 years).
- t. Biochemistry samples must be taken after fasting for at least 10 hours (6 hours for Week 2 and Week 6) for measurement of phosphate, calcium, creatinine, and lipids. If applicable, participants should bring their study intervention with them to each visit and have that day's intake at the site with food.
- u. The following criteria will trigger additional unscheduled visits: Platelet counts: <100,000 cells/mm3 or <100 GI/L or reduction from baseline by at least 50%; Hemoglobin: Decrease of at least 2 g/dL from baseline or at least Grade 2 (DAIDS); Reticulocytes: Reduction to <0.5% of the RBC count; Neutrophil count: Treatment emergent reduction to at least Grade 2 (DAIDS). (See also to Section 8.3.6.4, Hematologic Abnormalities).

In case any one of the above criteria are met, a confirmatory visit should be scheduled as soon as possible, preferably within 7 days of the receipt of the initial results. Confirmation of the results will trigger weekly or biweekly (every other week) unscheduled visits until improvement or stabilization of the respective parameter(s). Stabilization is defined as no further significant reduction over two consecutive visits

- v. Creatinine clearance (eGFRcr calculated by the CKD EPI formula) and eGFRcys calculated with the CKD EPI cystatin C formula will be assessed.
- w. Intervention emergent ALT/AST elevations (ie, ALT and/or AST \geq 3x ULN and \geq 3x nadir [ie, lowest value during study participation]), should trigger an assessment of confounding factors (alcohol intake, change in concomitant medication, and comorbidities) and a confirmatory visit, to be scheduled preferably within 7 days of the receipt of the initial ALT/AST results, to repeat laboratory testing of AFP, ALT, AST, ALP, bilirubin (total and direct), INR, albumin, and HBV DNA. Additional tests should be considered based on clinical judgement. For more details and further management guidance, refer to Section 10.6, Appendix 6, Intervention emergent ALT/AST Elevations.
- x. Urinalysis by dipstick: specific gravity, pH, glucose, protein, blood, ketones, bilirubin, urobilinogen, nitrite, leukocyte esterase, and microscopic analysis if needed. The dipstick reading should be done as soon as possible and in accordance with the manufacturer's recommendation. In case of a positive dipstick result, a urine sample will be set aside for additional examination of the positive parameter (eg, quantification as applicable).
- y. Urine chemistry sample (quantitative measurement): creatinine, sodium, phosphate, glucose, protein, and albumin.
- z. Urine sample for selected renal biomarkers including retinol binding protein and beta 2 microglobulin.
- aa. Additional samples may be collected for AFP testing in case of ALT flares.
- bb. For postmenopausal women only: an FSH level in the postmenopausal range may be used to confirm a postmenopausal state in women not using hormonal contraception or hormonal replacement therapy. However, in the absence of 12 months of amenorrhea, a single FSH measurement is insufficient to confirm a woman is not of childbearing potential (see Section 10.8, Appendix 8, Contraceptive and Barrier Guidance and Collection of Pregnancy Information).
- cc. Only applicable to participants who are enrolled at a site with an on site Fibroscan device. A Fibroscan assessment will only be done at baseline if it was not done at screening.
- dd. HBcrAg and HBV RNA samples may be batched and only selected samples may be tested at the sponsor's request. Samples can be used for assessment of other serologic/virologic markers of HBV.
- ee. Samples may be sequenced based on the sponsor virologist's request, considering the HBV DNA levels. In case of a virologic flare, additional samples for viral sequencing may be taken
- ff. Exploratory serology samples may be analyzed at the sponsor's discretion. Samples may be used to assess virologic or serologic markers of HBV.
- gg. All participants will have sparse PK sampling for JNJ 3989, NA, and PegIFN α2a. Bioanalysis of NA and PegIFN α2a is optional at the discretion of the sponsor. Bioanalysis of JNJ 6379 may also be done on samples collected from participants who received JNJ 6379 up to Protocol Amendment 5.
  For all samples, the date and time of the preceding 2 intakes of NA, the date and time of the previous JNJ 3989 administration, the date and time of the previous PegIFN α2a administration (if applicable), and the date and time of PK sampling should be recorded.
- hh. One sample at any time between 2 and 8 hours after JNJ 3989 dosing. Before leaving the study site, the participant's well being should be confirmed.
- ii. All participants who consent to participate in the intensive PK substudy (optional) will undergo intensive PK sampling at Week 24. If necessary (eg, for operational reasons), this visit may be scheduled at Week 28 or 32. The study intervention should be taken on site and time of dosing should be recorded. Pharmacokinetic samples will be taken predose and 15 minutes, 30 minutes, 1, 2, 3, 4, 6, 8,\* 10,\* and 24 hours post JNJ 3989 dose (\*the 8 and 10 hours postdose samples are optional). All efforts will be made to obtain the PK samples at the exact nominal time relative to dosing. However, samples obtained within 20% of the nominal time from dosing (eg, +/ 12 minutes of a 60 minute time point) will not be captured as a protocol deviation if the exact time of the sample collection is noted on the source document and data collection record (eg, CRF).
- ii. Sparse PK sampling is not required for participant with intensive PK sampling at the same visit.
- kk. PBMC samples will be collected at selected sites only. Additional PBMC samples may be taken in case of ALT flares, upon discussion with the sponsor, and may require an unscheduled visit.
- II. These samples are optional and will only be collected from participants who consent separately to this component of the study. The pharmacogenomic (DNA) sample should preferably be collected at baseline.
- mm. Adverse events and concomitant medications will be monitored from the time a signed and dated ISA ICF is obtained until completion of the participant's last ISA related procedure.
- nn. Exclusion criterion A25 regarding contraindications to the use of PegIFN α2a needs to be checked again at the end of the induction phase prior to the first dose of PegIFN α2a. If a participant's clinical status changes (including any available laboratory results or receipt of additional medical records) after screening but before the first dose of PegIFN α2a is given such that he or she meets exclusion criterion A25, then the participant should continue their study intervention until completion of the consolidation phase without the addition of PegIFN α2a.
- oo. The liver ultrasound does not need to be repeated at baseline if it was done at screening or within 6 months prior to screening.

- pp. As of Protocol Amendment 6, new participants will enroll without randomization to receive JNJ 3989+NA for 36 weeks (induction phase) and will then enter the 12 week consolidation phase during which they will have PegIFN  $\alpha$ 2a added to their treatment regimen.
- qq. Includes close monitoring for neuropsychiatric adverse events during the PegIFN α2a treatment period. Participants who develop a neuropsychiatric adverse event during PegIFN α2a treatment, will be monitored closely until the neuropsychiatric adverse event resolves, with frequent (at least weekly) follow up phone calls.
- rr. Most participants enrolled before Protocol Amendment 6 was in effect, have received JNJ 6379 as part of their study intervention. Dispensation of JNJ 6379 stopped immediately with the removal of JNJ 6379 as study intervention through an urgent safety measure. Participants have to return JNJ 6379 tablets to the site at the next scheduled visit.

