- a. All follow up study visits are to be scheduled relative to the last dose of JNJ 3989/PegIFN α2a. An unscheduled visit can be performed upon the investigator's discretion, in case of HBV DNA elevations, ALT elevations, other signs of worsening of liver disease, or for any other reason during follow up.
- Participants who withdraw consent during follow up will be offered an optional safety follow up visit.
- c. Participants who discontinue study intervention early will have an early WD visit and will enter follow up unless they withdraw consent. Participants who withdraw consent during study intervention will be offered an optional safety follow up visit to occur on the day of consent withdrawal. For the optional safety follow up visit, assessments are at the investigator's discretion and could be similar to the early WD visit.
- d. Follow up Week 8, 16, 20, 28, 32, 40, and 44 visits are not required for participants who did not complete NA treatment at Follow up Week 2 and for participants who have restarted NA treatment during the follow up period, provided that their HBV DNA and ALT values are stable.
- e. In between study visits, participants will take NA orally at home and will bring their NA with them to each study visit. At study visits, NA should be taken on site. PegIFN α2a should be administered weekly, preferably in the evening by self injection. If desired, participants can also choose to have the weekly administration of PegIFN α2a performed on site irrespective of the time of day. PegIFN α2a should preferably be administered in the evening prior to the sparse PK visit, or alternatively in the morning of the visit on site.

- f. No JNJ 3989/PegIFN α2a will be administered or dispensed during follow up. Administration/Dispensation of NA is only applicable for participants who could not stop NA treatment, or for those who met the NA re treatment criteria. In between study visits, participants will take NA at home and they will bring their NA treatment with them to each study visits, the NA treatment should be taken on site.
- g. If the NA treatment completion criteria are met at consolidation Week 12, treatment with NA will be completed at FU Week 2.
- h. Complete physical examination, including body weight, skin examination, and other body systems.
- i. Vital signs include supine SBP, DBP, pulse rate, and body temperature.

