If a participant withdraws prematurely, the reason for withdrawal (if known) is to be documented in the case report form (CRF) and in the source document. Participants who withdraw consent will be offered an optional safety follow-up visit (this visit should be performed within 2 month of withdrawal).

The Schedule of Activities summarizes the frequency and timing of efficacy, safety, and other assessments applicable to the Master Protocol PLATFORMPAHPB2001 and this ISA.

A DRC will be established for this study (Section 9.6, Data Review Committee). In addition, an IFLEP will be appointed (Section 9.7, Independent Flare Expert Panel).

A diagram of the study design is provided in Section 1.2, Schema.

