# 7. DISCONTINUATION OF STUDY INTERVENTION AND PARTICIPANT DISCONTINUATION/WITHDRAWAL

If a participant discontinues study intervention for any reason before consolidation Week 12, the participant will have an early withdrawal visit and will enter follow-up unless he/she withdraws consent. If the reason for withdrawal from the study is withdrawal of consent, then the participant will be offered an optional safety follow-up visit. Study intervention assigned to the participant who discontinued study intervention may not be assigned to another participant.

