	Cohort 2: Participants receive PegIFN- <math>\alpha</math>2a: Date of first PegIFN- $\alpha$ 2a intake  Participants who did not receive PegIFN- <math>\alpha</math>2a: Date of any study agent intake after Week 36 visit date  Otherwise: Missing	Cohort 2: Participants who did not withdraw from the study prior to the Consolidation Week 12 visit date: Min{Max[last intake date of any study agent (excluding NA), CW12], JNJ-3989 discontinuation date a } + 5 days a or cut-off date b , whichever occurs first  Participants who withdrew from the study prior to the Consolidation Week 12 visit date: Min[JNJ-3989 discontinuation date a , early study withdrawal visit date] + 5 days a or cut-off date b , whichever occurs first  Otherwise: Missing
Follow-up	Participants who did not withdraw informed consent during induction or consolidation phase: Max[End date of induction phase, End date of consolidation phase] +1  Otherwise: Missing	Max[study discontinuation date, study completion date] or cut-off date b , whichever occurs first  Otherwise: Missing

a Addition of 5 days is only applicable for JNJ-3989 discontinuation due to Adverse Events and Concomitant Medications.

b Cut-off dates will be defined to match the prespecified timepoints for DRC safety monitoring, interim analyses and the primary and final analyses, respectively.

c CW = Consolidation Week

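### The optional safety visit after consent withdrawal has two different timings, and SAP Table 1 leaves data dated after an early withdrawal outside every analysis phase

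*Protocol*

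**What the plan says.** Timing of the visit:

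- Protocol 1.3.1, footnote f: "Participants who withdraw consent will be offered an optional safety follow up visit to occur on the day of consent withdrawal".
- Protocol 1.3.2, footnote c: "Participants who withdraw consent during study intervention will be offered an optional safety follow up visit to occur on the day of consent withdrawal".
- Protocol 4.1, on the same optional visit: "this visit should be performed within 2 month of withdrawal".
- Protocol 7, where consent is withdrawn: "then the participant will be offered an optional safety follow-up visit". No timing is given.
- Protocol 1.3.2, for withdrawal later on: "Participants who withdraw consent during follow up will be offered an optional safety follow up visit". Again no timing is given.

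Data collection: the schedule footnote on adverse events has them monitored "until completion of the participant's last ISA related procedure". Protocol 8.3.1 refers to the Master Protocol for the collection period.

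Analysis:

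- SAP Table 1 gives a follow-up phase to "Participants who did not withdraw informed consent during induction or consolidation phase" and sets it to missing for everyone else.
- For those who leave early, the same table ends the last phase at the earliest of JNJ-3989 discontinuation and the early withdrawal visit; in induction the Week 36 visit (up to Week 60 in Cohort 1) is a further candidate. Five days may be added, subject to a footnote, and the data cut-off is a cap.
- SAP 6.1.2 allocates an adverse event to the phase whose start and stop dates contain its start date.
- SAP 6.2.1 derives worst-case laboratory values within each phase.
- SAP 6 has safety assessments presented by phase and cohort.

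**The concern.** A site that reads the schedule and a site that reads Section 4.1 will handle the same participant differently. One sees the participant on the day of withdrawal; the other may do so weeks later. Protocol 2.3.3 lists the option of safety follow-up after consent withdrawal among the measures that limit risk, so its timing should not depend on which section is consulted.

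The SAP adds a second difficulty. If the visit is held later, as Section 4.1 permits, its findings are dated after the participant's last phase has closed and there is no follow-up phase to receive them. I found no rule for data in that position. Safety is the first-listed secondary objective, and the by-phase tables are where a reader will look for incidence.

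**Working it through.** No power or alpha calculation is involved. I applied Table 1 as date arithmetic to a Cohort 2 participant who withdraws consent in induction before Week 36 and before any PegIFN-α2a.

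**Inputs**

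- Phase end = min(JNJ-3989 discontinuation date, early withdrawal visit date, Week 36 visit date), plus 0 or 5 days (SAP Table 1).
- Latest visit under Section 4.1 = withdrawal + 2 months, which is 59 to 62 days depending on the calendar months.
- Visit under the schedule footnotes = withdrawal + 0 days.
- The JNJ-3989 discontinuation date could be the withdrawal date or the last injection. With dosing every 4 weeks, I take the last injection as up to 27 days earlier. Both readings are shown as assumptions.
- The 5-day extension is shown both ways, because the Table 1 footnote can be read as restricting it by reason for discontinuation or by type of data.

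**Formula:** days from phase end to visit = (withdrawal − discontinuation date) + (visit − withdrawal) − extension, with a floor of 0.

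| Discontinuation date | Extension | Same-day visit | Visit at 2 months |
|---|---|---|---|
| Withdrawal date | 0 | 0 | 59 to 62 |
| Withdrawal date | 5 | 0 (0 − 5, floored) | 54 to 57 |
| Last injection, 27 days earlier | 0 | 27 | 27 + 59 = 86 to 27 + 62 = 89 |
| Last injection, 27 days earlier | 5 | 27 − 5 = 22 | 81 to 84 |

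An adverse event that starts in one of these gaps has no phase under SAP 6.1.2. A laboratory value taken at the visit has no phase under SAP 6.2.1. On the last-injection reading this applies even to a same-day visit.

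SAP 2.4 counts the period up to at least the last JNJ-3989 dose + 28 days as on-treatment. If the phase closes at the last injection, 28 days of that period (28 − 5 = 23 with the extension) lie outside any phase, so the unallocated data can include events that the SAP itself calls on-treatment.

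**How many participants.** The plan takes 33 in Cohort 2 with 10% dropout: 33 × 0.9 = 29.7, which reproduces its 30 evaluable. The loss is 33 × 0.1 = 3.3, so about 3. That is a ceiling. It counts dropout for any reason up to the FU Week 24 endpoint, whereas the affected group must have withdrawn consent during treatment, accepted an optional visit and had something recorded after the phase end. No dropout rate is stated for Cohort 1.

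**The case against.** The strongest reply is that little is lost:

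- **The timings overlap.** A same-day visit also lies within 2 months, so one visit can satisfy both texts. This stands, but a visit on any later day meets Section 4.1 and breaches the schedule, so the instructions still differ.
- **Reporting does not depend on phases alone.** The SAP 6.1.1 definition of a treatment-emergent event has no end date. Serious, related, grade 3 or higher, discontinuation-causing and special-interest events are listed separately, and so are treatment-emergent laboratory abnormalities (SAP 6.1.2, 6.2.2). This stands: what is lost is the by-phase summary, not all trace of the event.
- **Flares.** A reader might infer that post-treatment flares would go uncounted. The documents do not support that. SAP 5.3.1.1.9 classifies flares by on- or off-treatment status and accepts a criterion met at the last observed time point as confirmed, and SAP 5.3.2.1.7 summarises them by cohort. The Table 1 rule does not remove them.
- **Safety follow-up.** A reader might also infer that it necessarily stops on the day of withdrawal. That cannot be shown. Protocol 2.3.3 keeps safety follow-up procedures open to those who withdraw consent and has clinically significant abnormalities at early discontinuation followed to resolution or stabilization. The collection period is set in a Master Protocol section that is not available here.
- **Who is affected.** Not everyone who withdraws consent lacks a follow-up phase. Those who withdraw during follow-up have one.

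**Conclusion.** The point holds as an internal contradiction on visit timing plus a gap in SAP Table 1. Adverse events and laboratory values dated after the last phase ends, in participants who withdraw consent in induction or consolidation, belong to no phase and are left out of the by-phase summary tables. With a visit at the 2-month limit the uncovered interval is 54 to 62 days if JNJ-3989 discontinuation is dated at withdrawal, and 81 to 89 days if it is dated at an injection 27 days earlier.

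The expected effect is small: a subset of at most about 3 participants in Cohort 2. Scaling the 10% up to all 60 participants is tempting, but the documents state that rate only for Cohort 2. Nor do they settle which visit timing is clinically appropriate. The visit is optional and, under footnote f, its assessments are at the investigator's discretion. The primary endpoint is not the subject of this point. It is still worth correcting, because the rule as written would leave out safety data already collected.

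**What to change.** 1. **Protocol:** reconcile footnote f of 1.3.1, footnote c of 1.3.2, Section 4.1 and Section 7 so that one timing is stated for the optional safety visit. The choice belongs to the sponsor.
2. **SAP Table 1:** for participants who withdraw consent in induction or consolidation and have later safety data, define a follow-up phase from the day after the last treatment phase ends to the last safety contact. This closes the gap however the discontinuation date and the 5-day extension are read. The end needs its own wording, because the present follow-up end uses the study discontinuation or completion date, which may precede the safety contact. The on- and off-treatment flare definitions can stay as they are.

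The cost is one protocol clarification, one added row in Table 1 and the matching programming. No procedure is added, and only data already collected are tabulated.
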